### **PDAI**

The PDAI will be assessed at Day 1 and Weeks 6 and 10. The separate domain scores and the overall score, together with their change from baseline, will be calculated at each visit and summarized by treatment group.

The change from baseline for each PDAI domain score and for the overall score, will be analysed using the same repeated measures ANCOVA model as for the mean number of bowel movements per day.

Estimates of the following proportions of subjects will be evaluated at Weeks 6 and Weeks 10:

- Those who achieve an overall PDAI score  $<5$
- Those who achieve an overall PDAI score  $<3$
- Histological Improvement, defined as a PDAI Histology Score  $\leq 1$  (for subjects with a baseline score  $>1$ ), or with at least a 2-point improvement from baseline
- Histological Healing, defined as a PDAI Histology Score of 0 for subjects that had a baseline subscore above 0.

Each of these proportions will be compared between treatment groups at each visit using a Cochran-Mantel-Haenszel test accounting for region. In addition, they will be analyzed using separate logistic regression models for Week 6 and Week 10. These models will include terms for region, treatment, sex, age group and the corresponding baseline PDAI score.

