### **1.3.2 Efficacy Analysis**

All efficacy analyses and summaries will be performed using the FAS. A confirmatory analysis of the primary efficacy parameter will be carried out using the PPS.

All statistical tests comparing the treatment groups will be two-tailed and at the 5% level of significance.

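### Histological Improvement and Histological Healing are not nested, and with the FAS as denominator subjects with a baseline histology score of 0 or 1 are fixed non-improvers

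*SAP*

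**What the plan says.** Section 1.3.2.2 (PDAI) lists four responder proportions at Weeks 6 and 10. Two are histological.

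- Improvement: "Histological Improvement, defined as a PDAI Histology Score" of 1 or less, with the bracketed qualifier "for subjects with a baseline score" above 1, "or with at least a 2-point improvement from baseline".
- Healing: "Histological Healing, defined as a PDAI Histology Score of 0 for subjects that had a baseline subscore above 0".

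Both are tested: "Each of these proportions will be compared between treatment groups at each visit using a Cochran-Mantel-Haenszel test accounting for region". Logistic models follow for each visit, with the baseline PDAI score as one of the terms. The section names no denominator for Improvement. The general rule in section 1.3.2 is "All efficacy analyses and summaries will be performed using the FAS", and the FAS definition in section 1.1.4 requires confirmed active pouchitis at baseline but sets no threshold on the histology score.

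**The concern.** Healing, complete resolution on this score, sounds like the stricter outcome, so one expects every healed subject to be improved as well. The two definitions do not deliver that for a subject who starts at 1. A results table could then show subjects who are healed but not improved.

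The second issue is the denominator. In the Healing rule the baseline condition covers the whole definition. In the Improvement rule it sits inside the first route only, so nothing takes low-baseline subjects out of the FAS. Kept in, their outcome is settled by definition in both arms. That pulls both reported rates down, narrows the difference between arms, and makes the baseline term in the logistic model partly describe who was able to respond. If the choice is left open until after unblinding, it becomes a data-dependent decision on a tested endpoint.

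**Working it through.** The SAP states no figure for these endpoints, so there is none to reproduce. The check has two parts.

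**1. The rules applied to every transition.** Let b be the baseline score and s the score at the visit.

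- Improved: (b > 1 and s ≤ 1) or (b − s ≥ 2).
- Healed: b > 0 and s = 0.

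The SAP does not give the score's range or step. Whole points from 0 are assumed, with maxima of 3, 4, 6 and 12 tried.

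| Change (b to s) | Route 1: b > 1 and s ≤ 1 | Route 2: fall ≥ 2 | Improved | Healed |
|---|---|---|---|---|
| 1 to 0 | no (b = 1) | no (fall of 1) | no | yes |
| 2 to 1 | yes | no (fall of 1) | yes | no |
| 2 to 0 | yes | yes | yes | yes |
| any b ≥ 2 to 0 | yes | yes | yes | yes |

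For every maximum tried:

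- 1 to 0 is the only transition that is healed but not improved.
- 2 to 1 is the only one-point fall that counts as improved.
- Baselines 0 and 1 can never be improvers, because the largest possible falls are 0 and 1 point.
- Baseline 0 can never be healed either.

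With half-point steps, 0.5 to 0 would be a second transition that is healed but not improved.

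**2. The denominator.** Let q be the share of FAS subjects with baseline 0 or 1, assumed equal in the two arms, and r the improvement rate among the others. With everyone kept in, the reported rate is r(1−q), and the difference between arms is (r_active − r_placebo)(1−q). The SAP gives neither q nor a histology response rate. For illustration only, r is set to 50% vs 20%, the rates that section 1.2 assumes for the co-primary endpoints, and q is varied.

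| q | Active: 0.50(1−q) | Placebo: 0.20(1−q) | Difference |
|---|---|---|---|
| 0% | 50% | 20% | 30 points |
| 5% | 47.5% | 19% | 28.5 points |
| 10% | 45% | 18% | 27 points |
| 20% | 40% | 16% | 24 points |
| 30% | 35% | 14% | 21 points |

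The ratio of the two rates stays at 50/20 = 2.5 throughout. The odds ratio does not: it is (0.50 × 0.80)/(0.50 × 0.20) = 4.0 at q = 0 and (0.40 × 0.84)/(0.60 × 0.16) = 3.5 at q = 20%.

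**The case against.** The strongest reply is that the text has a coherent reading. A score of 1 or less is the target state for Improvement. A subject who starts at 1 is already there and so is not a candidate. On that reading, a 1-to-0 subject is not evaluable for Improvement rather than a failure. This reading is open, and the sponsor may intend it. The SAP does not state it, however: the qualifier is tied to one route, and the general rule sends the analysis to the FAS.

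It is also fair to say that placing the qualifier on one route does not change who is counted as improved, because on a whole-point scale a fall of 2 already requires a baseline of at least 2. Only the denominator is left open.

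Three stronger readings are tempting and are not supported:

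- **That the two rules contradict each other.** They are separate endpoints, each computable for every subject, and the SAP nowhere says that Healing is a subset of Improvement. They are non-nested, with different eligible baselines.
- **That barring baseline 0 is a flaw in the rule.** No rule can show improvement from 0, and Healing excludes baseline 0 too. It matters only for the denominator.
- **That the trial loses important power.** The SAP makes no power claim for histology. Any power figure would rest on rates borrowed from the co-primary endpoints and on an assumed q. Comparing retention with exclusion of all baseline 0 and 1 subjects would also not measure the fix below, which keeps baseline 1. Fixed non-responders in both arms dilute the difference; they do not inflate false positives.

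**Conclusion.** The point holds as a minor one. Read literally, the Improvement rule scores complete resolution from 1 as not improved while crediting a fall from 2 to 1, and it keeps in the denominator subjects who cannot respond. The classification result rests only on whole-point scoring from 0 and does not depend on the score's maximum. The dilution is by the factor (1−q). Under the assumed 50% vs 20%, a 30-point difference is reported as 27 points at q = 10% and 24 points at q = 20%. Since q is not given, the actual size is unknown and could be small.

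The effect is confined to non-primary histology proportions at Weeks 6 and 10. The co-primary endpoints, the sample size and the type I error of the primary test are not affected.

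**What to change.** Amend section 1.3.2.2 (PDAI) before unblinding:

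- Compute both histology proportions in FAS subjects with a baseline PDAI Histology Score above 0.
- Keep the two existing routes to Improvement, and state that every subject who meets Healing also meets Improvement. Healing is then nested within Improvement, and nobody in the denominator is barred from responding.

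If the sponsor intends Improvement to apply only to subjects with baseline above 1, restrict the Improvement denominator to those subjects instead. A 1-to-0 subject is then reported as not evaluable for Improvement, and the different denominators of the two endpoints should be shown in the table.

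The cost is a sentence or so of SAP text and a slightly smaller denominator, with no new data. The blinded data review in section 1.4, which already covers finalising the SAP, is a natural point at which to do it.

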### **Quality of Life Questionnaire**

Quality of life is assessed using the CGQL (at baseline and Weeks 6, 10, 18 and 26) and EQ-5D-5L (at baseline, Week 6 and Week 10).

The change from baseline for each CGQL and EQ-5D domain score, and for the overall scores, will be summarized by study visit.

The Total CGQL Score and the EQ-5D Index score will be analysed using the same repeated measures ANCOVA model as for the mean number of bowel movements per day.

### **Pouchitis intervention**

The proportion of subjects, by week 26, who have not received any additional pouchitis treatment will be calculated and compared between the two treatment groups.

The time to first intervention (including POUCHITIS related surgery) will be calculated for each subject. The time will be calculated in days from the start of study treatment.

Subjects not requiring a rescue intervention during their treatment period will be censored at the time of stopping study treatment in the analysis. Kaplan-Meier curves will be presented and estimates of the probability of no “rescue” intervention at Weeks 3, 6 and 10 will be provided together with their 95% confidence intervals.

In addition, time to first “rescue intervention” will be analyzed using a Cox’s proportional hazards regression model including terms for region, treatment, sex, age group, and the baseline PDAI score.

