### **Urgency**

Urgency will be recorded for each bowel movement in the subject's diary as none (0), some urgency (1), great urgency (2), and subject soiled themselves, involuntarily (3). The frequency of each score in the 7 diary days prior to a study visit will be evaluated.

Changes from baseline in urgency score at week 6 will be summarized and compared between treatments.

The proportion of subjects recording urgency episodes with score 3 (fecal incontinence) after 3, 6 and 10 weeks of treatment will be analysed using logistic regression models including terms for region, treatment, sex, age group and baseline urgency.

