#### **1.3.4 OPEN LABEL ACCESS ANALYSIS**

The following safety analysis will be conducted in all subjects receiving at least a part of one dose

1. The number and proportion of subjects with AEs; (worsening of disease will also be evaluated separately)
2. Assessment of clinical laboratory parameters
3. Assessment of vital signs

The following efficacy analysis will be conducted in all subjects receiving at least 80% of a 42-night treatment course

1. Percentage of subjects who report response to open-label access alicaforsen.
2. Interval between previous and current treatment courses

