#### **1.4.1 PK Parameters**

Plasma PK parameters for alicaforsen will be evaluated as follows. All consenting subjects will provide single time-point plasma samples at Day 1, Week 3 and Week 6.

In addition, full plasma concentration-time curves will be generated from a subset of randomised subjects (24 subjects, approximately 12 on active treatment and 12 on placebo) at Day 1 and Week 6. Samples from subjects in the placebo group will NOT be analyzed.

In this subset of subjects, the following PK parameters, as a minimum, will be calculated for alicaforsen:  $C_{max}$ ,  $t_{max}$ ,  $t_{1/2}$ ,  $AUC_t$ ,  $AUC_{0-24}$ ,  $AUC_{0-\infty}$ , and  $\lambda_z$ .

The following pharmacokinetic parameters will be derived:

$C_{max}$	The peak plasma concentration.
$t_{max}$	The time of peak plasma concentration.
$t_{1/2}$	The terminal half-life calculated from the terminal slope of the log concentration-time curve.
AUC	The area under the concentration-time curve will be calculated using the trapezoid rule for the interval 0 to $t_n$ h (time $t_n$ is the time at which the last non-zero level was recorded), plus the area under the exponential curve from $t_n$ h to infinity. The linear trapezoidal method will be used up to $t_{max}$ , and the logarithmic method will be used for the plasma concentrations declining from $C_{max}$ . The area from the time of last measured concentration to infinity will be extrapolated using the following formula:

$$AUC_{t_n-\infty} = \frac{\hat{C}_n}{\lambda_z}$$

where  $\lambda_z$  is the elimination rate constant calculated from non-linear regression of the terminal portion of the plasma concentration time curve, and  $\hat{C}_n$  is the predicted value of the concentration at time  $t_n$ .

Alicaforsen concentration-time curves will be plotted for individual subjects and will be summarized at Day 1 and Week 6, with concentrations on both log and linear scales. Single time-point PK data will be tabulated and summarized for each subject at Day 1, Week 3 and Week 6. Summary statistics for these data will also be computed across subjects.

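### Time to first pouchitis intervention is censored when study treatment stops, so later first interventions are lost from the Kaplan-Meier and Cox analyses

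*SAP*

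**What the plan says.** All of the following is in SAP section 1.3.2.2, Pouchitis intervention, unless another section is named.

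- **Companion endpoint.** "The proportion of subjects, by week 26, who have not received any additional pouchitis treatment" is calculated and compared between arms.
- **Event.** "The time to first intervention (including POUCHITIS related surgery) will be calculated for each subject". Nothing limits the event to the treatment period.
- **Time origin.** "The time will be calculated in days from the start of study treatment".
- **Censoring.** "Subjects not requiring a rescue intervention during their treatment period will be censored at the time of stopping study treatment in the analysis". No other rule is given for the Kaplan-Meier or the Cox analysis.
- **Landmarks.** Kaplan-Meier probabilities of no rescue "intervention at Weeks 3, 6 and 10 will be provided together with their 95% confidence intervals".

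The SAP does not state the length of the blinded course, and its indirect evidence is mixed:

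- Section 1.3.4, on open-label access, refers to "all subjects receiving at least 80% of a 42-night treatment course".
- Section 1.4.1 says: "All consenting subjects will provide single time-point plasma samples at Day 1, Week 3 and Week 6".
- The Urgency text in section 1.3.2.2 has the proportion with incontinence episodes "after 3, 6 and 10 weeks of treatment will be analysed using logistic regression models".

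**The concern.** The endpoint is named and defined as time to first intervention, but the censoring rule turns it into time to first intervention while still on study drug. The SAP never labels it that way. A subject first treated at Week 14 fails the Week 26 endpoint, yet enters the Kaplan-Meier and Cox analyses as a censored observation from weeks earlier.

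Three things are at stake:

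1. **Horizon.** The time-to-event results do not cover the period of the companion proportion, so the two can disagree for reasons unrelated to the drug.
2. **Week 10 estimate.** If the blinded course ends before Week 10, the promised probability and confidence interval have no subjects at risk behind them.
3. **Informative censoring.** Stopping study drug is partly an outcome. A subject who stops for worsening and receives other treatment the next day is censored just before the event. Kaplan-Meier and Cox methods assume that censoring is unrelated to the risk of the event. If such stops differ by arm, the comparison can be biased. The SAP gives nothing from which to judge the size or direction.

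**Working it through.** **Plan figure.** The SAP states no event rate, event count, hazard ratio or power for this endpoint, so there is no figure to reproduce.

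**Step 1: what follows from the text alone.** Let S be the day a subject stops study treatment and X the day of first intervention.

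| Case | Week 26 proportion | Kaplan-Meier and Cox |
|---|---|---|
| X on or before S | intervention counted | event at X |
| S < X ≤ Week 26 | intervention counted | censored at S |
| no intervention by Week 26 | none | censored at S |

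The second row is the defect. It arises for any course that ends before Week 26.

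**Step 2: the Week 10 landmark.**

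- 42-night course: event-free subjects leave the risk set at about day 42. Week 10 is day 70, so none is at risk. The estimate is undefined or repeats the end-of-treatment value.
- 10-week course: Week 10 can be estimated, but events from Week 10 to Week 26 are still excluded.

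**Step 3: how many events could be lost.**

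Input from SAP section 1.2: 69 subjects per arm.

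Assumptions, none from the SAP:

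- Week 26 intervention rates p26 (placebo/alicaforsen) of 30%/15%, 40%/25% and 80%/60%.
- Weibull timing with shape k = 1 (constant hazard), 0.5 (front-loaded) or 0.3 (strongly front-loaded).
- No dropout, and everyone stops at week T = 6 or 10.

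Formulas:

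- Cumulative hazard: H(t) = −ln(1 − p26) × (t/26)^k
- Expected events by t: 69 × Σ over arms of [1 − exp(−H(t))]
- Share excluded: 1 − events(T)/events(26)
- Power (Schoenfeld, two-sided 5%, 1:1): Φ(|ln HR| × √(d/4) − 1.96), with d events

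Worked case, 40%/25%:

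- H(26) is 0.511 on placebo and 0.288 on alicaforsen, so HR = 0.288/0.511 = 0.56 and |ln HR| = 0.574.
- Events by Week 26: 69 × (0.40 + 0.25) = 44.9. Power: Φ(0.574 × √(44.85/4) − 1.96) = 48.5%.
- T = 6, k = 1: 6/26 = 0.231. Events: 69 × [1 − exp(−0.118)] + 69 × [1 − exp(−0.0664)] = 7.7 + 4.4 = 12.1. Excluded: 1 − 12.1/44.9 = 73%.

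| T | k | Events kept of 44.9 | Excluded | Illustrative power |
|---|---|---|---|---|
| 6 | 1 | 12.1 | 73% | 17% |
| 6 | 0.5 | 23.9 | 47% | 29% |
| 6 | 0.3 | 31.0 | 31% | 36% |
| 10 | 1 | 19.5 | 56% | 24% |
| 10 | 0.5 | 30.0 | 33% | 35% |
| 10 | 0.3 | 35.4 | 21% | 40% |

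Share excluded at the ends of the assumed range:

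| T | k | 30%/15% | 80%/60% |
|---|---|---|---|
| 6 | 1 | 74% | 64% |
| 6 | 0.5 | 48% | 36% |
| 6 | 0.3 | 32% | 22% |
| 10 | 1 | 58% | 46% |
| 10 | 0.5 | 35% | 24% |
| 10 | 0.3 | 22% | 14% |

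**Step 4: comparison with the SAP's other time-to-event endpoint.** Time to clinical remission, in the Stool Frequency part of section 1.3.2.2, is censored at the last assessment of the score, including for subjects who withdraw. The intervention endpoint departs from that approach without giving a reason.

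**The case against.** The strongest defence is that this is a deliberate on-treatment analysis beside a Week 26 proportion. The censoring sentence speaks of rescue during the treatment period, whereas the proportion speaks of additional pouchitis treatment. The landmarks stop at Week 10, and later interventions are still compared between arms through the proportion. Such a pair of analyses is possible. But the event definition has no on-treatment limit, the analysis is nowhere labelled on-treatment, and a Week 10 landmark would not fit that reading if the course is 6 weeks. The defence therefore supports keeping an on-treatment analysis under its own name, not the present text.

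Other objections stand in part:

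- **The Week 10 point is conditional.** The protocol may state the blinded course length. The 42 nights belong to open-label access, sampling times do not define a course, and the Urgency wording points to 10 weeks. The loss of later events does not depend on this.
- **The magnitudes rest on assumptions.** They show what is possible, not what will happen. At 40%/25% the comparison has under 50% power even with full follow-up. The SAP claims no power here, so the power figures carry no weight in the conclusion.
- **The endpoint is secondary or tertiary.** The SAP is to be finalised before unblinding (section 1.4), so correction is still possible.

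**Conclusion.** The censoring rule is wrong for the endpoint as the SAP defines it. From the text alone, any first intervention between stopping treatment and Week 26 counts against the subject in one analysis and cannot be an event in the other two. This needs no assumption beyond treatment ending before Week 26.

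The number of events lost cannot be fixed from the SAP. Across the assumed rates and timings it runs from about one in seven first interventions (10-week course, strongly front-loaded) to about three in four (6-week course, constant hazard). Whether the Week 10 estimate is empty depends on the blinded course length. Bias from informative censoring is plausible, with unknown size and direction.

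This should be fixed before unblinding. The co-primary analyses and their conclusions are not affected.

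**What to change.** Replace the censoring sentence with wording such as:

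> The event is the first additional pouchitis treatment or pouchitis-related surgery from first dose to Week 26. Subjects without an event are censored at Week 26, or at last contact if earlier. Stopping study treatment is not a reason for censoring.

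Then:

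- Add a Week 26 Kaplan-Meier estimate with its confidence interval to those at Weeks 3, 6 and 10.
- Use one defined term for the event in place of intervention, rescue intervention and additional pouchitis treatment. State how open-label alicaforsen is handled in this analysis if it can begin before Week 26.
- If an on-treatment analysis is also wanted, label it as such and restrict its landmarks to the treatment period.
- State the length of the blinded treatment period, or refer to the protocol for it, and bring the Urgency wording and the Week 10 landmark into line with sections 1.3.4 and 1.4.1 where they describe the same period.

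The cost is SAP wording and programming. Intervention status to Week 26 is already needed for the companion proportion; this analysis also needs the date of the first intervention over the same period.

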#### **1.3.2.3 Exploratory**

The exploratory analysis will include, but will not be limited to, the exploratory analyses specified in this protocol. Any exploratory analyses performed which were not specified in the protocol or the statistical analysis plan will be clearly described as such in the clinical study report.

### **Histology**

The change from baseline in histological score, assessed using the D’Haens score, will be measured at baseline, Weeks 6 and 10. Changes from baseline will be summarized.

### **Inflammatory markers**

The inflammatory marker CRP and WBC will be measured at Screening, Day 1 and Weeks 3 and 6. The change from baseline to Weeks 3 and 6 will be analysed

Faecal calprotectin will be measured at screening, Weeks 3, 6, 10, 18 and 26. The change from baseline will be summarized.

### **WPAI**

Scores derived from the WPAI (i.e. the percentage of worktime missed due to health issues, percentage of work impairment due to health issues, percentage activity impairment due to health issues, and the percentage productivity loss) will be suitably summarized by treatment group at each study visit.

#### **1.3.2.4 Subgroup analysis**

The primary endpoint will also be analysed in the following subgroups for consistency with the overall trial results.

- Gender
- Age group

Subjects who have previously failed antibiotics will be further categorized into those who were “efficacy” failures (failed to respond to initial therapy, or lost response to continued therapy) and those who failed due to intolerance. An appropriate summary/analysis of these subjects groups will be performed.

